### Minimizing probability of violence associated with participants' offering HIV testing to sexual partners:

To minimize the likelihood of social harms, including violence against HIV-positive pregnant women participants, trained study staff will talk to participants at the time of enrollment about the importance of *using their discretion* and *assessing the risk of intimate partner violence (IPV)* when deciding whether to introduce self-testing to their partners. Study staff will also talk to participants about strategies for introducing self-testing or voluntary counseling and testing (VCT) referral voucher to partners, including talking points. It will be emphasized to study participants that they are not obligated to distribute self-tests to their partners. Participants will be counseled to never offer a self-test or invitation letter to a partner who they will believe will become violent due to introducing HIV testing.

Having developed the training materials for study staff and implemented the intervention successfully in the Kenya pilot study, we are confident that these procedures help minimize the risks of social harms and intimate partner violence. We will also provide study participants with information on where they can seek help if they do experience violence or do need advice. We will establish a support telephone line (hotline) that study participants or their sexual partners can call at any time that will put them in touch with the study coordinator. The study coordinator will help arrange support for any woman experiencing violence. In our pilot study we set up a hotline similar to what is proposed here.

Minimizing probability of adverse reactions to test results and ensuring receipt of appropriate services: To ensure correct usage of self-tests (in the intervention group) and to minimize the probability of psychological distress due to HIV testing, we will include simple instruction materials with each self-test on how to use the tests, in English and Luganda. The self-test will include information listing VCT clinics in the area where free HIV testing and counseling is available, including the ANC clinic where his partner receives care and IDI Kasangati. Information will also be provided on clinics in the area where free HIV care and treatment is available. A support telephone line (hotline) will allow study participants or their sexual partner to call at any time in order to be in touch with study staff, who will be ready to provide additional information on where to seek further testing, care or treatment.

#### Partner invitation group

Women in the control arm will be provided invitation letters, the standard of care, to deliver to their partner to come for HIV testing to their ANC clinic for fast-track testing or at IDI Kasangati, alone or as a couple. As in the intervention group, each invitation letter will include positively framed messages to men about the opportunity to receive PrEP and ART if they get tested. Letters will also include information on how to contact a 24-hour "helpline" to talk with a counselor about the meaning of results and referrals. Invitation letters will have unique numbers to allow linkage of the man's testing to his partner. Letters will be collected at collaborating ANC clinics.

#### Antenatal and postnatal care

Data collection will occur during standard of care antenatal/postnatal visits. HIV-positive pregnant women will access routine care at antenatal clinics according to guidelines for preventing and treating HIV infection in Uganda [71]. Pregnant women will have up to 4 antenatal visits before delivery: 1 visit in the first trimester, 1 visit in the second trimester and 2 visits in the third trimester. The standard-of-care antenatal package includes cotrimoxazole preventive therapy, nutrition assessment, iron, folic acid and multivitamin supplementation and screening for syphilis. Women newly initiating ART in PMTCT B+ will have same-day pre-ART adherence counselling and ART initiation (Table 1). They will have PMTCT B+ follow-up visit two weeks after initiating ART, and monthly visits for ART refills thereafter until delivery. Women will be offered delivery at a facility of their choice. After delivery, women will be followed quarterly for up to 12 months.

Brief study questionnaires will be administered will occur at the PMTCT visits to avoid separate study-specific visits. Postnatal care and infant immunization visits will follow the routine maternal and child health (MCH) schedule. Viral load (VL) monitoring will include plasma HIV RNA levels at enrollment, 6 and 12 months post-partum. Blood samples will be batch-tested at collaborating laboratories. Women will be asked about interruptions in ART use. If the mother is stable on ART with good adherence and undetectable VL, post-partum visits will be quarterly thereafter. During clinic visits, women will complete interviewer-administered surveys to collect data on behavioral factors that could mediate women's post-partum use of ART. Women will be provided their viral load results at the next visit with counseling about the relationship between adherence, viral load and transmission risk.

#### Male partner procedures

Male partners of women enrolled in the study will be recruited using established recruitment methods for serodiscordant couples. These strategies operationalize protocol-specified requirements and ensure participant privacy for eligibility determination. Men will be referred to their partner's antenatal clinic or IDI Kasangati, either through invitation letters for HIV testing or following HIVST for confirmatory testing (Figure 4). Men will undergo informed consent for HIV testing and referral for HIV care and ART if they test HIV-positive or offered PrEP if they test HIV-

negative. Trained research staff will counsel potentially eligible men about possible participation in the study. Men who indicate a willingness to participate in the study for up to 12 months postpartum will be offered an opportunity to undergo study screening.

#### Figure 4: Study Procedures for Male Partners

#### Counseling about PrEP and ART

Participants will receive behavioral counseling on the effectiveness of ART and 6 months of PrEP to bridge to ART for HIV serodiscordant couples, post-partum ART continuation and adherence, PrEP benefits and adherence for HIV-negative male partners, and clinical and prevention benefits of ART for HIV-positive men. Counseling sessions will occur every 3 months, either to each partner individually or as a couple. Ad hoc sessions will be provided when requested by couples (Figure 5). Counselors will stress the importance of post-partum ART persistence with high adherence for clinical benefits and to prevent onward HIV transmission to breastfeeding infants and sexual partners.

Table 1. Components of HIV prevention delivery for HIV serodiscordant couples as
standard of care public health clinics & enhanced PMTCT B+ with integrated ART and
PrEP

• • = •	
SOC services for HIV	
serodiscordant couples	Additional components of integrated PrEP with PMTCT B+
Debeuienel ecurealiza	Couples: counseling on HIV serodiscordance & efficacy of
Benavioral counseling	Integrated PrEP and ART for (enroliment)
	HIV-positive women: counseling on post-partum ART
	continuation & adherence for women (antenatal visits, 3,6, 9 and
Condom provision	12 months)
PrEP counseling & provision	HIV-negative men: counseling about PrEP benefits & adherence (enrollment, guarterly visits through up to 12 months)

6-monthly CD4 testing	HIV-negative men: assessment of acute HIV infection, PrEP provision
	HIV-positive women: HIV RNA testing (enrollment, 6 & 12 months)
Annual HIV RNA testing, plus suspected virologic failure	HIV negative men:6-monthly renal function monitoring, blood archive for tenofovir testing (3 & 6 months) HIV-positive men: assessment of ART use

Counselors will assess men's willingness to initiate PrEP or ART, willingness of women to continue ART post-partum, strategies to maintain daily adherence to PrEP and ART, the timelimited use of PrEP, other HIV risk reduction strategies (condom use, medical male circumcision, and treatment of sexually transmitted infections), and couple communication. Male partners will be supported to make informed choices. Acute HIV symptoms will be assessed before PrEP dispensation. Medication refills with 3-month supplies, ART and PrEP adherence counseling, condoms, HIV testing, and lab monitoring (6-monthly creatinine, CD4 and HIV RNA testing) will be provided (Table 1).

#### PrEP medication and dispensation

PrEP will be offered to HIV-negative men according to national guidelines[71], and with the recommendation to take it for 6 months after their partner starts ART or until she is virally suppressed. Male partners will be assessed for acute HIV infection, counseled on PrEP and offered PrEP, if it is desired and there are no acute HIV symptoms. PrEP will be dispensed in a 3-monthly supply. HIV testing will be conducted at each quarterly visit prior to providing PrEP refills. PrEP use will be suspended if HIV tests are positive or if acute HIV infection is suspected. Renal monitoring will occur on a 6-monthly basis.

The study will provide open-label PrEP to HIV-negative male partners for 6 months or until their HIV-infected female partner is virally suppressed. Co-formulated FTC/TDF at 200 mg / 300 mg respectively will be used. The dose of FTC/TDF is the standard dose approved by the U.S. Food and Drug Administration. The study drug will be stored in accordance with the drug manufacturer's recommendations. The pharmacy and storage facility will have locked, climate-controlled environments, with controlled humidity and temperature to remain within limits allowed by the manufacturer for drug storage. Counseling on the medications being used, their side effect profiles, how to take the study medication, what to do if side effects are experienced, and the importance of not sharing study medication to optimize potential efficacy will be provided.

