#### SUMMARY

Uganda has the fifth highest HIV burden globally and one of the highest fertility rates in Africa. Prevention of mother-to-child HIV transmission Option B+ (PMTCT B+) is national policy in Uganda. To maximize the prevention and clinical benefits of PMTCT B+, the challenges of low HIV testing by male partners and high rates of post-partum discontinuation of antiretroviral therapy (ART), insufficient adherence, and incomplete viral suppression need to be addressed. Women may be more likely to continue ART long-term and have higher adherence post-partum if their partner is tested, there is mutual disclosure of HIV status, and their partner takes ART or PrEP, depending on his status. Innovative approaches are needed to allow men to test in settings other than busy antenatal clinics, preferably where they have privacy, are comfortable and do not miss work. Innovative HIV testing technology – HIV self-testing (HIVST) could increase male partner engagement in HIV testing, and uptake of prevention and care services through linkage to highly effective pre-exposure prophylaxis (PrEP) and ART for all HIV-positive men. This study has been designed to address this gap through an enhanced PMTCT B+ program with HIV self-testing, and linkage to PrEP or ART, for male partners.

In a demonstration project we recently completed among mutually disclosed East African HIV serodiscordant couples (the Partners Demonstration Project), integrated ART and PrEP delivery with time-limited PrEP for the HIV-negative partner as a 'bridge' until the HIV-positive partner was on ART for six months, and achieved viral suppression, was very acceptable, achieved very high uptake and adherence to ART and PrEP, and nearly eliminated HIV transmission. This protocol builds on that demonstration project by evaluating whether PMTCT outcomes are improved by increasing uptake of HIV testing and PrEP among HIV-negative men whose pregnant partner is HIV-positive. PrEP for HIV-negative male partners of HIV-positive pregnant women provides highly effective prevention benefits during an important 'season of risk' when men may have higher HIV acquisition risk from their partner if she is viremic (during the first few months after ART initiation, post-partum ART discontinuation or due to viral resistance), or from outside partners.

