We will conduct a randomized trial to evaluate whether provision of oral HIV self-test kits to HIVpositive pregnant women overcomes male partners' reluctance to be tested in PMTCT clinics. Pregnant women will be trained in the use and interpretation of HIVST and given two oral fluidbased HIVST kits to use with or give to their partners, along with information about HIV testing and prevention and care services. We will offer men confirmatory testing regardless of their HIV test result through HIVST, counseling, and if negative, PrEP and if positive, ART. We will provide counseling to minimize social harms of HIV self-testing, and additional counseling and referral to social support services when social harms occur. This project will address key challenges in PMTCT B+ programs, by evaluating innovative strategies to increase male partner involvement coupled with offering PrEP to HIV-negative men, ART to HIV-positive men, and encouraging postpartum ART continuation and adherence among HIV-positive women.

Design:	Randomized clinical trial Up to 12 months of post-partum follow-up
Population:	HIV-positive pregnant women in Kampala, Uganda who have a male partner of unknown HIV status (approximately 500 women in total)
Study Sites:	Infectious Diseases Institute (IDI) Kasangati and collaborating antenatal care (ANC) clinics in Kampala, Uganda

Approach: We will recruit HIV-positive women ≥18 years accessing PMTCT B+ programs in Kampala, who have a male partner of unknown HIV status. Women will be randomized to the intervention (HIVST) or the control arm (invitation letters to deliver to partners to come to the ANC clinic where she receives care or IDI Kasangati for HIV testing). Women will be instructed in the use and interpretation of HIVST and be provided two HIVST kits to give to or use with their male partners. We will recommend that HIV-negative men use PrEP until their partner has been on ART for at least 6 months, and that HIV-positive men take ART. Specifically, PrEP as a bridge to ART will be offered to HIV-negative male partners as follows: when the HIV-positive pregnant partner is not yet taking ART, PrEP will be offered, and when the HIV-positive pregnant partner initiates ART, PrEP will be provided for the HIV-negative male partner for six months (i.e., when viral suppression in the HIV-positive partner would be expected to be typically achieved). This bridge to ART approach is detailed in Figure 1.

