#### **Specific Aims**

# Aim 1: Determine whether an enhanced PMTCT program with HIV self-testing for male partners and provision of PrEP to HIV-negative male partners increases the proportion of male partners who test for HIV and men who initiate PrEP.

Innovations are needed to reach male partners for HIV testing that allow men to test where they are comfortable, which typically is not in busy antenatal clinics. Provision of HIV self-tests (HIVST) to pregnant women for their partners is safe, acceptable, and effective, and could facilitate partner testing, and increase uptake of PrEP by HIV-negative men and ART by HIV-positive men. HIVST is a promising approach to increasing partner and couples testing, which has not yet been evaluated in the context of PMTCT B+ programs. We will randomize 500 HIV-positive women initiating PMTCT B+ in Kampala in a 2:1 ratio to one of two partner testing strategies: 1) HIVST kits (intervention) to give to or use with their partner, or 2) invitation letters for fast-track testing at the clinic (standard of care). Men who test will be offered confirmatory testing and counseling. Men who test HIV-positive will be linked to ART, and men who test HIV-negative will be offered PrEP for the first six months after his partner initiates ART through PMTCT.

The co-primary outcomes are the proportion of male partners who test for HIV and the proportion of HIV-negative male partners who initiate PrEP.

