#### STUDY METHODS

#### Overall design

This is a randomized trial of HIV-positive pregnant women and their partners. The overall goal is to evaluate the impact of innovative strategies on male partner HIV testing, and engagement in HIV care and prevention among men, on post-partum ART continuation and adherence among HIV-positive women. We will recruit HIV-positive women in PMTCT B+ programs in Kampala to be randomized to: 1) the intervention arm in which they receive HIVST kits for their partners with self-instruction materials about HIVST, encouragement to seek confirmatory testing and counseling along with a voucher and referral, and brief educational materials about PrEP and ART, or 2) the control arm in which they receive invitation letters to deliver to their partners that invite men to fast-track HIV testing at the clinic, along with brief educational materials about PrEP and ART. Women in the intervention arm will be instructed in the use and interpretation of HIVST and be provided two HIVST kits to give to or use with their male partners. Male partners will receive an educational brochure outlining the benefits of HIV testing and ART or PrEP. We will receive an educational brochure outlining the benefits of HIV testing and ART or PrEP. We will recommend that HIV-negative men use PrEP until their partner has achieved viral suppression, and that HIV-positive men take ART.

The co-primary outcomes of the study are the proportion of male partners who test and the proportion of HIV-negative male partners who take PrEP. The primary analysis is an intent to treat comparison by randomization arm of the primary outcome: proportion of women whose male partners who test HIV-uninfected and initiate PrEP within six months after their HIV-positive partner is randomized. A secondary outcome is an objective marker of PrEP adherence - tenofovir detection at 3 and 6 months - among men who initiate PrEP.

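### The rule for ending PrEP is worded four ways, so a man could be advised to stop while his partner is still viraemic

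*Protocol*

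**What the plan says.** The current text gives four duration rules.

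- **Six months of her ART only.** Protocol, Summary (Approach): "We will recommend that HIV-negative men use PrEP until their partner has been on ART for at least 6 months". The same paragraph then describes provision for six months from her ART start and explains six months as the time by which suppression is usually expected. Aim 1, in both Specific Aims and Objectives: "men who test HIV-negative will be offered PrEP for the first six months after his partner initiates ART through PMTCT". The Benefits section ends free access six months after she starts ART. Counseling about PrEP and ART mentions six months of PrEP with no start point.
- **Suppression only.** Overall design says the study will "recommend that HIV-negative men use PrEP until their partner has achieved viral suppression".
- **Either.** PrEP medication and dispensation does this twice: the recommendation to the man ("take it for 6 months after their partner starts ART or until she is virally suppressed") and the study supply ("for 6 months or until their HIV-infected female partner is virally suppressed"). The second gives no start point for the six months.
- **Both.** The SAP's Protocol Summary (Methodology) asks for at least six months of ART together with suppression.

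The initial offer in the dispensing section is open: a man is "offered PrEP, if it is desired and there are no acute HIV symptoms". SAP 3.4.1 also sets no time limit on the offer.

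The Summary describes the predecessor project's bridge as lasting "until the HIV-positive partner was on ART for six months, and achieved viral suppression". It justifies PrEP here because "men may have higher HIV acquisition risk from their partner if she is viremic", and the same sentence adds risk from outside partners.

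**The concern.** Six months on ART stands in for suppression. The two agree for most women, and for them the differences in wording do little harm. They part for the woman who is still viraemic at ART month 6, and her partner is the man the bridge is meant to protect. For him some sections imply stopping and others imply continuing, and the section that staff would dispense from is the least clear.

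A second ambiguity comes from the Aim 1 wording. It can be read as closing the offer itself six months after she starts ART, whereas the dispensing section offers PrEP to any HIV-negative man who tests. Late testers are foreseeable: the SAP's Protocol Summary lets men enrol up to 12 months post-partum, and the eligibility criteria do not require women to be new to ART.

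**Working it through.** **Step 1. Apply each wording to one case: she is viraemic at ART month 6.**

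| Wording | Where | Advice to him |
|---|---|---|
| Six months of ART only | Summary (Approach), Aim 1 (twice), Benefits | Stop (the 'at least' in Approach permits longer but does not require it) |
| Suppression only | Overall design | Continue |
| Either, whichever first | PrEP medication and dispensation | Stop |
| Either, whichever later | PrEP medication and dispensation | Continue |
| Both | SAP Protocol Summary | Continue |

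The advice turns on which section is followed, and no section is said to govern.

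**Step 2. Number of men.** The plan gives no figure for this, so there is none to reproduce. Inputs from the Protocol's Sample size section (Tables 3 and 4): 500 women; overall test uptake 43% with 60% of men HIV-negative, or 53% with 70% HIV-negative; 80% PrEP uptake; 95% retention.

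PrEP starters = women × tested × HIV-negative × uptake × retention

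- Low: 500 × 0.43 × 0.60 × 0.80 × 0.95 = 98
- High: 500 × 0.53 × 0.70 × 0.80 × 0.95 = 141

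The documents give no viraemia rate at ART month 6, so two background figures serve as proxies:

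- 4%: the predecessor project reports 96% suppression at 12 months in women who started ART in pregnancy.
- 10%: PMTCT B+ in Uganda reports 90% undetectable after more than six months of ART.

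Men with a viraemic partner: 98 × 0.04 = 3.9 to 141 × 0.10 = 14.1, or about 4 to 14. The background also cites 23% virologic failure among post-partum women randomised to continue ART. That rate would give 98 × 0.23 = 23 to 141 × 0.23 = 32. It describes a different group, so it is shown only as a sensitivity figure.

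**Step 3. When a study viral load would be available.** This sets the cost of requiring a documented result. Samples after enrolment fall at 6 and 12 months post-partum (Antenatal and postnatal care; Table 5; SAP 3.4.2), and women get results at the next visit. Assumptions: ART starts at enrolment, delivery is at week 40, a month is 4.345 weeks, trimesters are as in SAP 6.3.1, and the earliest and latest starts are weeks 8 and 38.

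ART month at the 6-month sample = (40 − start week) / 4.345 + 6; the result comes 3 months later.

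| ART start (week) | Sample (ART month) | Result (ART month) | Months past ART month 6 |
|---|---|---|---|
| 8 to 14 | 13.4 to 12.0 | 16.4 to 15.0 | 10.4 to 9.0 |
| 15 to 27 | 11.8 to 9.0 | 14.8 to 12.0 | 8.8 to 6.0 |
| 28 to 38 | 8.8 to 6.5 | 11.8 to 9.5 | 5.8 to 3.5 |

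With 3-month refills, the wait is two to four refills for first- and second-trimester starters (6.0/3 = 2.0 to 10.4/3 = 3.5) and about two for third-trimester starters (3.5/3 = 1.2 to 5.8/3 = 1.9). These waits are on the long side: staff may see the result before she does, and routine clinic results may come sooner.

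**The case against.** The best reply is that this is one bridge concept written in shorthand. The Approach paragraph itself links six months to expected suppression and says at least six months. Table 6 allows PrEP as indicated at months 9 and 12. Table 1 lists quarterly PrEP counselling through up to 12 months. The dispensing section defers to national guidelines, and its only suspension triggers are a positive test or suspected acute infection. The SAP wording is a summary rather than a dispensing instruction, and the predecessor project's rule is not this trial's rule. The approach is also said to be detailed in Figure 1, which was not available for this check.

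Much of that stands. It rules out the strong reading that a reader might infer, namely that the protocol tells staff to stop PrEP at month 6 in a viraemic couple. No section says so. But none of this text settles the case either: 'at least' sets no end, 'as indicated' states no indication, and the guideline reference is followed by the study's own either/or recommendation.

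Two other inferences also fail. One is that PrEP need not be offered once she has had six months of ART and is suppressed. That would narrow the open offer, ignore the outside-partner risk named in the Summary, and remove some HIV-negative men from those who can have the Aim 1c event. The other is that a new viral load at ART month 6 is needed. The protocol also mentions 6-monthly HIV RNA testing (not tied to ART start) and routine testing for suspected failure, late third-trimester starters have a study sample near that time, and any documented result would do.

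**Conclusion.** The inconsistency is real and sits in current text. It matters for participant protection and consistent conduct: under the time-only wording, or the either/or read as whichever is first, a man could be advised to stop while his partner is viraemic. About 4 to 14 men is a rough guide. It rests on the planning values and on two viraemia rates borrowed from other groups and times. It counts men exposed to conflicting wording, not men who would in fact be stopped.

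A reader might infer that the Aim 1 result is at risk. The documents do not support that: the Aim 1 endpoint is PrEP initiation, not duration. The share of men who test after her ART month 6 is not given, so no effect of the offer wording on uptake can be estimated or claimed. The change is worth making because it is cheap and adopts a rule that the SAP summary already states.

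**What to change.** In PrEP medication and dispensation, keep the offer open to every HIV-negative man who tests. Replace both duration statements with one: PrEP continues until his partner has had at least six months of ART, counted from her ART start, and has a documented viral load below 400 copies/ml from any study or routine result, whichever is later, subject to national guidelines. The threshold is the protocol's own Aim 2 definition of suppression.

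Bring six further protocol sections into line with this and with the SAP's Protocol Summary: Summary (Approach), Specific Aims (Aim 1), Overall design, Objectives (Aim 1), Counseling about PrEP and ART, and Benefits. In the two Aim 1 statements, also remove the reading that the offer closes six months after she starts ART. Do not make the initial offer depend on her suppression status. No study procedure, analysis or table needs to be added.

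The cost is wording in seven protocol sections and a check against the cited national guideline. Some men will stay on PrEP for a few more 3-month refills while a viral load result is awaited: two to four at most on the timing above, fewer where a routine result exists. A man whose partner remains viraemic would stay on longer, within the study's follow-up.
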